4.1.5 Blinding and procedures for unblinding

This Phase I trial will be handled in an open fashion throughout (that is, during the conduct, including data cleaning and preparation of the analysis). This is considered acceptable because the potential for bias seems to be low and does not outweigh practical considerations.

Emergency envelopes will not be provided, because the dose of trial medication is known to investigators and subjects.

PK samples will be labelled in such a way that treatment allocation cannot be derived by the analytical site.

4.1.6 Packaging, labelling, and re-supply

BI 425809 tablets will be provided by BI. They will be packaged and labelled in accordance with local law and the principles of Good Manufacturing Practice.

For details of packing and the description of the label, refer to the ISF.

The telephone number of the sponsor and the name, address and telephone number of the trial site are provided in the subject information form. The EudraCT number is indicated on the title page of this protocol as well as on the subject information and informed consent forms.

For donepezil, the commercially available product will be supplied by a public pharmacy. Transport and storage are under the responsibility of the investigator and must comply with the pertinent information in the SmPC of the drug product used in the clinical trial [[R18-3913](#)].

Documentation on the commercial drug product, containing at least the following information, must be available on-site in the ISF:

- Clinical trial number
- Investigator name
- Trade name of drug product
- Substance International non-proprietary name (INN)
- Holder of marketing authorization
- Dosage form
- Quantity
- Unit strength
- Batch/lot number
- Use-by date
- Point of purchase
- Date of receipt
- Recipient (name and function)

In addition, documentation of drug purchase, including identification of drug product and quantity, must be available at the clinical site and filed in the ISF.

Also, if required according to the SmPC of the drug product, documentation of temperature monitoring during shipment/transport must be available at the clinical site and filed in the ISF (e.g. for commercial drug products required to be stored cooled or frozen).

No re-supply is planned.

4.1.7 Storage conditions

Drug supplies will be kept in their original packaging and in a secure limited access storage area in accordance with the recommended (labelled) storage conditions. If necessary, a temperature log must be maintained to make certain that the drug supplies are stored at the correct temperature. If the storage conditions are found to be outside the specified range, the local clinical monitor (as provided in the list of contacts) is to be contacted immediately.

4.1.8 Drug accountability

The investigator or designee will receive the investigational drugs delivered from the sponsor following requirements are fulfilled:

- Approval of the clinical trial protocol by the IRB / ethics committee
- Availability of a signed and dated clinical trial contract between the sponsor and the investigational site
- Approval/notification of the regulatory authority, e.g. competent authority
- Availability of the *curriculum vitae* of the Principal Investigator
- Availability of a signed and dated clinical trial protocol

Only authorised personnel documented in the form 'Trial Staff List' may dispense medication to trial subjects. The trial medication must be administered in the manner specified in the CTP.

The investigator or designee must maintain records of the product's delivery to the trial site, the inventory at the site, the use by each subject, and the disposal of unused products. These records will include dates, quantities, batch / serial numbers, expiry ('use-by') dates, and the unique code numbers assigned to the investigational medicinal product and trial subjects, as applicable. The investigator or designee will maintain records that document adequately that the subjects were provided the doses specified by the CTP and reconcile all investigational medicinal products received from the sponsor. At the time of disposal of remaining trial medication, the investigator or designee must verify that no remaining supplies are in the investigator's possession.

All unused medication will be disposed of locally by the trial site upon written authorisation of the trial clinical monitor. Receipt, usage and disposal of trial medication must be documented on the appropriate forms. Account must be given for any discrepancies.

4.2 OTHER TREATMENTS, EMERGENCY PROCEDURES, RESTRICTIONS

4.2.1 Other treatments and emergency procedures

No specific rescue medication is foreseen for BI 425809.

In case of a donepezil overdose, general supportive measures should be utilised. Tertiary anticholinergics such as atropine may be used as an antidote for donepezil overdosage. Intravenous atropine sulphate titrated to effect is recommended. An initial dose of 1.0 to 2.0 mg i.v. with subsequent doses based upon clinical response.

No additional treatment is planned. However, in case of adverse events in need of treatment, the investigator can authorise symptomatic therapy. In those cases, subjects will be treated as necessary and, if required, kept under supervision at the trial site or transferred to a hospital until all medical evaluation results have returned to an acceptable level.

4.2.2 Restrictions

4.2.2.1 Restrictions regarding concomitant treatment

In principle, no concomitant therapy is allowed, including hormonal contraceptives or ovary hormone replacement.

However in case there are AEs needing treatment special care is to be taken that the following concomitant medications should be avoided:

- The use of weak, moderate or strong CYP3A4 inhibitors and inducers is not permitted. CYP3A4 sensitive drugs with narrow therapeutic range are not permitted during the trial period.
- Drugs that are known to trigger gastrointestinal bleeding/ulcers, e.g. NSAIDs or corticosteroids, are not allowed in Part 2.
- Paracetamol and diclofenac must be avoided as symptomatic therapy of AEs due to its potential liver toxicity.
- The concomitant use of other inhibitors of acetylcholinesterase, agonists or antagonists of the cholinergic system is also not allowed. An exception is the use of tertiary anticholinergics such as atropine in case of overdose (see [Section 4.2.1](#)).

All concomitant or rescue therapies will be recorded (including time of intake on study days) on the appropriate pages of the CRF.

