Regarding donepezil, no inhibition of the metabolism of drugs metabolized by CYP-450 isoenzymes is expected at therapeutic doses of donepezil ([Section 1.2.2](#)).

In summary, a clinically relevant pharmacokinetic interaction causing elevated exposures of donepezil or BI 425809 is considered unlikely.

Safety measures

- Close monitoring of
 - Adverse events
 - Safety lab (special focus on hepatic parameters, markers of GI bleeding (CRP, haematology, iFOB), CK)
 - ECG (focus on possible vagotonic action of donepezil)
 - Vital signs
- Prohibition to use drugs as concomitant therapy that are known to also trigger gastrointestinal ulcers/hemorrhage, e.g. NSAIDs ([Section 4.2.2](#))
- Availability of rescue medication (atropine) in case of signs and symptoms of cholinergic crisis (see [Section 4.2.1](#)).
- Subjects will receive a trial specific emergency card with information for anesthesiologists about the donepezil intake in case of unplanned surgery and potential use of succinylcholine
- As donepezil may impact the ability to operate vehicles and/or machines, subjects participating in Part 1 of this trial subjects are not allowed to drive a vehicle or operate machines during Visit 3
- Although only healthy subjects are allowed to enter this trial per se the investigator has to specifically ask subject's for any life-time history of asthma or seizure resulting in exclusion of the subject

Although rare, a potential for drug-induced liver injury is under constant surveillance by sponsors and regulators. Therefore, this study requires timely detection, evaluation, and follow-up of alterations in selected liver laboratory parameters to ensure subjects' safety.

Overall assessment

Considering the good safety profile of BI 425809 observed so far in healthy subjects, and the safety and tolerability of donepezil up to single doses of 23 mg in healthy volunteers, the unlikelihood of increased drug exposures due to a donepezil-BI 425809 interaction and taking into account the safety measures described in this chapter, the benefit of a successful clinical development of BI 425809 for the treatment of Alzheimer's disease or CIAS is assessed to outweigh the potential risks to healthy subjects participating in this trial that are further considered to be low and acceptable.

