3. DESCRIPTION OF DESIGN AND TRIAL POPULATION

3.1 OVERALL TRIAL DESIGN AND PLAN

The study will consist of two parts and will be performed in healthy male and female subjects. Each subject does only participate in one part of the trial. Both parts are designed as open-label, two-treatment, two-period, one fixed sequence cross-over to investigate the effects of donepezil as perpetrator (Part 1) and as victim (Part 2) in relation to BI 425809.

Part 1 and part 2 are independent from each other as they investigate different pharmacokinetic objectives and endpoints of part 1 would not alter the rationale for part 2. Therefore completion of part 1 is not required to allow start of part 2. This of course does not apply for any safety issues as defined in the stopping criteria (ref [Section 3.3.4](#)).

Considering the well-known safety profiles of the selected dose of BI 425809 and donepezil, the unlikelihood of increased drug exposures due to a donepezil-BI 425809 interaction and the already implemented safety measures (ref [Section 1.4](#)) treatment of all subjects in one cohort per trial part, i.e. one cohort of 18 subjects in part 1 and one cohort of 14 subjects in part 2, respectively, is not considered to be an undue risk for enrolled subjects. However, treatment in cohorts for logistical reasons is possible. In this case, the cohorts should be of about the same size and be treated not too wide apart in terms of time for better comparability and reducing any possible factors influencing the readout.

In both parts there will be no washout period between treatments.

An overview of all relevant trial activities is provided in the [Flow Chart](#). For visit schedule and details of trial procedures at selected visits, refer to [Sections 6.1](#) and [6.2](#), respectively.

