20. A marked baseline prolongation of QT/QTc interval (such as QTc intervals that are repeatedly greater than 450 ms in males or repeatedly greater than 470 ms in females) or any other relevant ECG finding at screening
21. A history of additional risk factors for *Torsade de Pointes* (such as heart failure, hypokalaemia, or family history of Long QT Syndrome)
22. Subject is assessed as unsuitable for inclusion by the investigator, for instance, because the subject is not considered able to understand and comply with study requirements, or has a condition that would not allow safe participation in the study

Female subjects will not be allowed to participate, if any of the following apply:

23. Positive pregnancy test, pregnancy, or plans to become pregnant within 30 days after study completion
24. Lactation

In addition, the following trial-specific exclusion criteria apply:

25. History of asthma or obstructive pulmonary disease
26. Clinically relevant cardiac conduction disorders such as sinoatrial or higher degree atrioventricular block and sick sinus syndrome.
27. Bladder outflow obstruction
28. Subjects with increased risk for developing gastrointestinal ulcers (e.g. those with a history of ulcer disease or frequent use of non-steroidal anti-inflammatory drugs)
29. History of macular degeneration or any abnormal finding in visual tests (Amsler grid test, colour discrimination test) at screening
30. Subjects with known hypersensitivity to piperidine derivatives (e.g. astemizol, loratadin, pethidin, loperamid, haloperidol, domperidon)
31. Liver tests (ALT, AST, GGT, AP), Total Bilirubin or Creatinine outside the normal range at the screening examination

Specifically for Part 2:

32. Any suicidal ideation of type 2 to 5 on the C-SSRS in the past 12 months (i.e. active suicidal thought, active suicidal thought with method, active suicidal thought with intent but without specific plan, or active suicidal thought with plan and intent)
33. Any lifetime history of suicidal behaviour (i.e. actual attempt, interrupted attempt, aborted attempt, or preparatory acts or behaviour).

For study restrictions, refer to [Section 4.2.2](#).

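### The ban on drugs that can cause gastrointestinal bleeding or ulcers is limited to Part 2 in Section 4.2.2.1, against the unrestricted ban in Section 1.4, and omits Part 1, where donepezil is given daily for 28 days

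*Protocol*

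**What the plan says.** Protocol Section 4.2.2.1 opens with a general rule: "In principle, no concomitant therapy is allowed, including hormonal contraceptives or ovary hormone replacement". It then makes an exception for adverse events that need treatment and lists the drugs to be avoided in that case. One item reads: "Drugs that are known to trigger gastrointestinal bleeding/ulcers, e.g. NSAIDs or corticosteroids, are not allowed in Part 2". Another, with no limit to a part, reads: "Paracetamol and diclofenac must be avoided as symptomatic therapy of AEs due to its potential liver toxicity". Section 4.2.1 confirms that the exception is real: "in case of adverse events in need of treatment, the investigator can authorise symptomatic therapy".

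Protocol Section 1.4, under its safety measures, lists "Prohibition to use drugs as concomitant therapy that are known to also trigger gastrointestinal ulcers/hemorrhage, e.g. NSAIDs". It refers to Section 4.2.2 and names no part. The driving ban in the same list is expressly tied to Part 1, Visit 3.

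**The concern.** Two sections of one protocol give different scopes for the same safety rule, and the narrower one is the list a site would consult when choosing a treatment. The limitation also falls on the unexpected side, because Part 1 is where donepezil is given repeatedly.

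Three things are at stake:

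- **Choice of treatment.** An investigator treating an adverse event in Part 1 gets a different answer from the restriction list than from the benefit-risk section.
- **The safety argument.** The overall benefit-risk judgement is reached "taking into account the safety measures described in this chapter". Section 3.1 also cites the Section 1.4 measures among its reasons for dosing each part together: "one cohort of 18 subjects in part 1 and one cohort of 14 subjects in part 2, respectively, is not considered to be" unduly risky.
- **Handling of the data.** Protocol Section 7.3 names use of restricted medication as a possible reason to exclude PK data, and SAP Table 6.2: 1 (code D1) makes prohibited medication a possible reason for exclusion from the PK set. Whether an NSAID given in Part 1 counts as prohibited depends on which section is read.

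**Working it through.** The protocol states no figure on this point to reproduce. The check compares the texts, with some simple arithmetic.

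**1. Scope of the rule.** Section 1.4 sets no limit by part, although it names a part elsewhere in the same list when it means one. Section 4.2.2.1, to which it refers, limits the rule to Part 2. No reason for the narrower scope is given in the text available.

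**2. Where the donepezil exposure lies** (Sections 4.1.1 and 4.1.4):

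| | Doses per subject | Total donepezil |
|---|---|---|
| Part 1 | 7 × 5 mg + 21 × 10 mg = 28 daily doses | 35 + 210 = 245 mg |
| Part 2 | 2 × 10 mg, as two single doses | 20 mg |

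The Part 1 total agrees with Table 4.1.4: 1. The ratio is 245 / 20 = 12.25, so the explicit ban covers the part with about one-twelfth of the donepezil. Section 1.2.2 lists gastric and duodenal ulcers and gastrointestinal haemorrhage among donepezil's effects.

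**3. Where the monitoring lies** (Flow Charts, footnote 10 in Part 1 and footnote 5 in Part 2). Faecal occult blood tests in Part 1:

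- screening: 1
- Visit 2, Days 5 and 8: 2
- Visit 3, Days 4, 8, 12, 16, 19, 22, 25 and 29: 8
- end of trial: 1

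That makes 1 + 2 + 8 + 1 = 12. Part 2 has 2, at screening and end of trial. The sponsor's own monitoring places the gastrointestinal concern in Part 1.

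**4. What the literal text leaves open.** Under the adverse-event exception, paracetamol and diclofenac are to be avoided in both parts. Other NSAIDs and corticosteroids fall under the gastrointestinal bullet, which stops at Part 2.

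**5. How often the exception might arise (illustration only).** Section 1.2.2 reports drug-related headache in 22.2% of the 18 Part 1 subjects in the sponsor's earlier donepezil interaction trial.

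- 0.222 × 18 = 4 subjects
- Clopper-Pearson 95% interval for 4/18: 6.4% to 47.6%
- Expected number among the 18 subjects here: 18 × 0.2222 = 4.0, with limits 18 × 0.0641 = 1.2 and 18 × 0.4764 = 8.6

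These limits are for the expected count; the count actually seen could vary more. At the lower limit, for example, the chance of no headache at all in 18 subjects is 0.936^18, about 30%. The calculation assumes that the earlier rate carries over, although that trial also gave a different sponsor compound. The documents do not say how many headaches needed treatment.

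**The case against.** The best defence is that the two sections can both be obeyed. Section 4.2.2.1 does not permit NSAIDs or corticosteroids in Part 1; it is silent on them. The general ban and the Section 1.4 prohibition still apply to all 18 subjects, so an investigator who follows the broader text breaks no rule. Other controls also act in Part 1: the investigator must authorise symptomatic therapy, diclofenac is barred, exclusion criterion 28 removes ulcer-prone subjects and frequent NSAID users, and occult blood is tested repeatedly.

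This shows that the gap is small, not that it is absent. The bullets exist to govern the exception to the general ban, so the general ban does not fill a hole in them. A list that names Part 2 alone invites the reading that Part 1 is free of the restriction. Criterion 28 acts only at screening, and occult blood testing detects bleeding without preventing the exposure.

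Four further points are fair and limit what can be claimed:

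- The headache figure does not count treated headaches, still less those treated with an NSAID.
- Section 3.1 also rests on the known safety profiles and the unlikelihood of raised exposure, so its conclusion is not shown to depend on this one measure.
- The link to donepezil is inferred, and the non-clinical safety section for BI 425809 is cut short in the public copy, so a reason specific to Part 2 cannot be ruled out entirely. The dosing and the occult blood schedule point the other way.
- No PK endpoint, model or confidence interval is defined by this wording.

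**Conclusion.** The concern holds. Section 4.2.2.1 is inconsistent with Section 1.4, and as written it omits the part with the greater donepezil exposure. This should be fixed because it is a safety rule with the wrong scope. Its practical reach is limited to the treatment of adverse events in the 18 Part 1 subjects with an NSAID other than diclofenac or with a corticosteroid.

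No size of risk is claimed, since the documents give neither a gastrointestinal bleeding rate nor a rate of adverse events needing treatment. The textual conflict itself needs no assumption. The view that the ban belongs in Part 1 at least as much as in Part 2 rests on reading donepezil as its target. Whether the limitation to Part 2 was a slip for Part 1 cannot be settled from the documents.

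**What to change.** Delete the limitation to Part 2 from the bullet in Protocol Section 4.2.2.1, or name both parts, and notify the site. Section 1.4 needs no change. The SAP needs none either, because code D1 refers generally to prohibited medication and will follow the corrected protocol.

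The direct cost is a one-phrase amendment and a site notice, with no effect on endpoints or sample size. There are two consequences to accept. NSAID or corticosteroid use in Part 1 becomes an explicit prohibited-medication deviation, which could lead to a subject's exclusion from the PK set when cases are decided at the Report Planning Meeting. And with paracetamol already barred, NSAIDs are expressly removed as an option for pain or headache in Part 1, as they already are in Part 2; the protocol names no permitted analgesic for either part.

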4.2.2.2 Restrictions on diet and life style

While admitted to the trial site the subjects are restricted from consuming any other foods or drinks than those provided by the staff. Standardised meals will be served at the time points described in the [Flow Chart](#).

Part 1:

On all dosing days of Part 1, with the exception of PK profile days, the trial medication will be administered after a fasting period of at least 2 h prior and keeping a post-administration fasting period of at least 1 h. Fluid intake is not allowed from 1 h predose until administration.

On PK profile days (Day 1, Visit 2 and Day 22, Visit 3) subjects will remain fasted for at least 4 hours before administration until 4 hours after and their fluid intake is restricted to the water administered with the drug and an additional 240 mL of water served at 2 h and 4 h post-dose (mandatory for all subjects) from 1 hour before drug intake until 4 hours post dose.

On PK profile days (Day 1, Visit 2 and Day 22, Visit 3) subjects are requested to go to bed after dinner, lie down (i.e. no declination of the upper body of less than 45 degrees from upright posture except for medical examination or if they need to go to the toilet) and try to sleep. For details regarding post-dose bed resting period see [Flow Chart](#).

Part 2:

In Part 2, administration will be performed following an overnight fast starting no later than 10 h before scheduled dosing. On PK profile days (Day 1, treatment C and Day 10, treatment D), no food is allowed for at least 4 h; from 1 h before drug intake until lunch, fluid intake is restricted to the water administered with the drug, and an additional 240 mL of water served at 2 h and 4 h post-dose (mandatory for all subjects). From lunch until 24 h post-dose, total fluid intake is restricted to 3000 mL. On the remaining days, food is not allowed for at least 1 h after drug administration and fluid intake is not allowed from 1 hour predose until administration.

On PK profile days (Day 1, Visit 2 and Day 10, Visit 3) subjects are not allowed to lie down, i.e. no declination of the upper body of more than 45 degrees from upright posture, except for ECG and blood pressure measurements, during the first 4 h after drug administration.

Part 1 + 2:

On all other in-house days food will be served at standard times if not indicated otherwise in the [Flow chart](#).

Alcoholic beverages, grapefruits, Seville oranges (sour or bitter oranges) and their juices, and dietary supplements and products including St. John's wort (*Hypericum perforatum*) are not permitted starting 7 days before the first administration of trial medication until after the last PK sample of each study period is collected.

Smoking is not allowed during in-house confinement at the trial site.

Methylxanthine-containing drinks or foods (such as coffee, tea, cola, energy drinks, and chocolate) are not allowed from 24 h before until 24 h after each administration of trial medication.

Excessive physical activity (such as competitive sport) should be avoided starting 7 days before the first administration of trial medication until the end of trial examination.

Direct exposure to the sun or exposure to solarium radiation should be avoided during the entire study.

If female subjects of child-bearing potential are included in the trial, adequate contraception is to be maintained throughout the course of the trial (see [Section 3.3.2](#) for the definition of adequate measures). Hormonal contraception is not allowed.

